5.0 METHODOLOGY

5.1 Study Population

5.1.1 Participant Inclusion Criteria

Participants are eligible to be included in the study only if all of the following criteria apply:

1. Male/female participants who are at least 18 years of age on the day of signing informed consent with histologically confirmed diagnosis of melanoma or RCC and untreated metastatic brain disease will be enrolled in this study.

Male participants: A male participant must agree to use a contraception as detailed in Appendix 3 of this protocol during the treatment period and for at least 120 days after the last dose of study treatment and refrain from donating sperm during this period.

Female participants: A female participant is eligible to participate if she is not pregnant (see Appendix 3), not breastfeeding, and at least one of the following conditions applies:

- a. Not a woman of childbearing potential (WOCBP) as defined in Appendix 3

OR

- b. A WOCBP who agrees to follow the contraceptive guidance in Appendix 3 during the treatment period and for at least 120 days after the last dose of study treatment.

2. The participant (or legally acceptable representative if applicable) provides written informed consent for the trial.
3. Have histologic or cytologic confirmation from any body site of metastatic melanoma irrespective of BRAF mutation status or renal cell carcinoma irrespective of histologic subtype.
4. Patients who have had prior resection or biopsy of a CNS and/or extracranial metastasis will be required to provide a formalin-fixed, paraffin embedded (FFPE) specimen from tumor taken at the time of surgery, if available. Fresh biopsies of a metastatic lesion should be performed if clinically able.

Note: Participants are not required to have new or repeat brain metastasis biopsies for enrollment on the trial.

Note: For those who have never had CNS brain metastasis biopsies, tissue of an accessible extracranial lesion will be obtained pre-treatment, unless deemed not possible by the treating physician and upon discussion with PI. In this case, archival extracranial metastatic tissue will be suitable.

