5. Have at least one brain metastasis that is at least 5 mm AND twice the MRI slice thickness, but less than or equal to 3 cm, which is asymptomatic, has not been previously radiated, and is not requiring immediate local therapy or steroids. Lesions situated in a previously irradiated area are considered allowed if measurable per the aforementioned criteria and if progression has been demonstrated. Patients with any lesion(s) >3 cm can be enrolled provided the following: (1) the lesion must receive local treatment prior to initiation of study drugs (either by stereotactic radiosurgery or resection), (2) the patient is not symptomatic from the lesion(s) once local therapy has been administered, and (3) at least one additional, non-treated lesion between 5 mm and 3 cm is still present.
6. Prior treatment for either the Melanoma or RCC cohorts may include:
Patients must have received at least 2 doses of an anti-PD-1/PD-L1 drug at some point in their treatment course. Any number of prior treatments including PD-1/PD-L1 inhibitors are allowed. Anti-PD-1/PD-L1 does not have to be the most recent therapy. Patients with melanoma who developed brain metastasis within 6 months of the last dose of adjuvant anti-PD-1 can be enrolled.
7. Life expectancy of at least 3 months.
8. A history of radiotherapy for brain metastases is allowed up to 1 week before study treatment provided that neurologic sequelae are resolved, and that measurable untreated target lesion(s) remain.
9. Have an Eastern Cooperative Oncology Group (ECOG) performance status of 0 to 1. Evaluation of ECOG is to be performed within 7 days prior to the date of allocation.
10. Adequately controlled blood pressure (BP) with or without antihypertensive medications, defined as a systolic BP ≤ 150 or a diastolic BP ≤ 90 mmHg at screening and on Cycle 1 Day 1.

Note: Eligibility of a participant that is receiving ≥ 3 antihypertensive medications prior to study entry will require PI approval.
11. Have adequate organ function as defined in the following table (Table 1). Specimens must be collected within 10 days prior to the start of study treatment.

12. Table 1 Adequate Organ Function Laboratory Values

System	Laboratory Value
Hematological	
Absolute neutrophil count (ANC)	$\geq 1500/\mu\text{L}$
Platelets	$\geq 100\,000/\mu\text{L}$
Hemoglobin	$\geq 9.0\text{ g/dL}$ or $\geq 5.6\text{ mmol/L}^a$
Renal	

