22. Has urine protein ≥ 2 g/24-hour.

Note: Participants with $>1+$ proteinuria on urine dipstick will undergo 24-hour urine collection for quantitative assessment of proteinuria.
23. Evidence of a bleeding diathesis, risk for severe hemorrhage, or clinically significant coagulopathy.
24. Uncontrolled hypertension (systolic BP >150 mmHg or diastolic BP >90 mmHg) in spite of an optimized regimen of antihypertensive medication.

25. Has a history of (non-infectious, non-radiation-induced) pneumonitis not responsive to steroids or has current pneumonitis. Patients will also be excluded if there are respiratory issues including active infection or require supplemental oxygen for activities of daily living.
26. Has an active infection requiring systemic therapy.
27. Has a known history of Human Immunodeficiency Virus (HIV).
28. Has a known history of Hepatitis B or known active Hepatitis C virus infection.

Note: No testing for Hepatitis B and Hepatitis C is required unless mandated by local health authority.

29. Has a history or current evidence of any condition, therapy, or laboratory abnormality that might confound the results of the study, interfere with the subject's participation for the full duration of the study, or is not in the best interest of the subject to participate, in the opinion of the treating investigator.
30. Has known psychiatric or substance abuse disorders that would interfere with cooperation with the requirements of the trial.
31. Is pregnant or breastfeeding or expecting to conceive or father children within the projected duration of the study, starting with the screening visit through 120 days after the last dose of trial treatment.
32. Women of child-bearing potential who are unwilling to or unable to use an acceptable method of contraception to avoid pregnancy for the entire study and for at least 5 months after cessation of study drug or have a positive pregnancy test at screening or baseline, or who are pregnant or breast feeding.

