5.2.2.4 Management of AEs associated with lenvatinib

Lenvatinib dose reduction and interruption for participants who experience lenvatinib- related toxicity that are not considered irAEs will be in accordance with the dose modification guidelines described in Table 5. An interruption of study treatment for more than 28 days will require PI consultation and approval before treatment can be resumed.

Adverse events will be graded using NCI CTCAE v5.0. For presumed non irAEs, investigators will decide the probability of the event being related to lenvatinib and whether dose modification or interruption/discontinuation, as applicable, of one or both drugs is required. The starting dose of lenvatinib is 20 mg/day for participants enrolled. Dose reductions of lenvatinib occur in succession based on the previous dose level (14, 10, and 8 mg/day). Any dose reduction below 8 mg/day must be discussed with the PI. Once the study drug dose has been reduced, it may not be increased at a later date, unless the dose was mistakenly decreased; in this situation, PI's approval is required to increase the dose.

Refer to the subsections below for management of hypertension (Section 5.2.2.6), proteinuria (Section 5.2.2.7), diarrhea (Section 5.2.2.8), hepatotoxicity (Section 5.2.2.9), thromboembolic events (Section 5.2.2.10), posterior reversible encephalopathy syndrome/reversible posterior leukoencephalopathy syndrome (PRES/RPLS; Section 5.2.2.11), hypocalcemia (Section 5.2.2.12), and hemorrhage (Section 5.2.2.13), as appropriate, before consulting the dose modification table (Table 5).

- BP should be well-controlled prior to the start of lenvatinib. Blood pressure should be monitored after 1 week of treatment with lenvatinib, then every 2 weeks for the first 2 months and at the beginning of each cycle thereafter while on treatment. If a patient develops systolic BP ≥ 150 mmHg or diastolic BP ≥ 90 mmHg active management is indicated.
- Urine protein should be monitored regularly. If urine dipstick $\geq 2+$ is detected, dose interruptions, adjustments, or discontinuation may be necessary. Discontinue in the event of nephrotic syndrome.
- Monitor and correct all electrolyte abnormalities in all patients.
- Liver function tests should be monitored before initiation of treatment, then every 2 weeks for the first 2 months and monthly thereafter during treatment. In the case of hepatotoxicity, dose interruptions, adjustments, or discontinuation may be necessary.

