5.2.2.6 Management of Hypertension

Hypertension is a recognized side effect of treatment with drugs inhibiting VEGF signaling. Investigators should therefore ensure that participants enrolled to receive treatment with lenvatinib have BP of $\leq 150/90$ mm Hg at the time of study entry and, if known to be hypertensive, have been on a stable dose of antihypertensive therapy for at least 1 week before Cycle 1 Day 1. Early detection and effective management of hypertension are important to minimize the need for lenvatinib dose interruptions and reductions.

Regular assessment of BP should be as detailed in the Study Flow Chart (Section 6.1). Hypertension will be graded using NCI CTCAE v5.0, based on BP measurements only (and not on the number of antihypertensive medications). If the participant's initial BP measurement is elevated (ie, systolic BP ≥ 140 mm Hg or diastolic BP ≥ 90 mm Hg), the BP measurement should be repeated at least 5 minutes later.

One BP assessment is defined as the mean value of 2 measurements at least 5 minutes apart. If the BP assessment (ie, the mean of the 2 BP measurements obtained at least 5 minutes apart) is elevated (systolic BP ≥ 140 mm Hg or diastolic BP ≥ 90 mm Hg), a confirmatory assessment should be obtained at least 30 minutes later by performing 2 measurements (at least 5 minutes apart) to yield a mean value.

Antihypertensive agents should be started as soon as elevated BP (systolic BP ≥ 140 mm Hg or diastolic BP ≥ 90 mm Hg) is confirmed on 2 assessments at least 30 minutes apart. The choice of antihypertensive treatment should be individualized to the participant's clinical circumstances and follow standard medical practice. For previously normotensive participants, appropriate antihypertensive therapy should be started when systolic BP ≥ 140 mm Hg or diastolic BP ≥ 90 mm Hg is first observed on 2 assessments at least 30 minutes apart. For those participants already on antihypertensive medication, treatment modification may be necessary if hypertension persists.

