Lenvatinib should be withheld in any instance where a participant is at imminent risk to develop a hypertensive crisis or has significant risk factors for severe complications of uncontrolled hypertension (eg, BP $\geq 160/100$ mm Hg, significant risk factors for cardiac disease, intracerebral hemorrhage, or other significant co-morbidities). Once the participant has been on the same antihypertensive medications for at least 48 hours and the BP is controlled, lenvatinib should be resumed as described below.

Participants who have had systolic BP ≥ 160 mm Hg or diastolic BP ≥ 100 mm Hg must have their BP monitored on Day 15 (or more frequently as clinically indicated) until systolic BP has been ≤ 150 mm Hg and diastolic BP has been ≤ 95 mm Hg for 2 consecutive treatment cycles. If a repeat event of systolic BP ≥ 160 mm Hg or diastolic BP ≥ 100 mm Hg occurs, the participant must resume the Day 15 evaluation until systolic BP has been ≤ 150 mm Hg and diastolic BP has been ≤ 95 mm Hg.

Hg for 2 consecutive treatment cycles. Participants will have the option of having BP measurements between visits obtained locally by a health care professional. A diary will be provided as a tool to aid the participant in collecting blood pressure evaluations between study visits.

The following guidelines should be followed for the management of systolic BP ≥ 160 mm Hg or diastolic BP ≥ 100 mm Hg confirmed on 2 BP assessments at least 30 minutes apart:

- Continue study drug and institute antihypertensive therapy for participants not already receiving antihypertensive therapy. Note: Eligibility of a participant that is receiving ≥ 3 antihypertensive medications prior to study entry will require PI approval.
- For those participants already on antihypertensive medication, the dose of the current agent may be increased, if appropriate, or 1 or more agents of a different class of antihypertensive should be added. Study treatment can be continued without dose modification.
- If systolic BP ≥ 160 mm Hg or diastolic BP ≥ 100 mm Hg persists despite maximal antihypertensive therapy, then lenvatinib administration should be interrupted and restarted at 1 dose level reduction only when systolic BP ≤ 150 mm Hg and diastolic BP ≤ 95 mm Hg and the participant has been on a stable dose of antihypertensive medication for at least 48 hours.

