10.0 ADMINISTRATIVE AND REGULATORY

Multicenter Management and Coordination

The YCCI MCU will support the Sponsor-Investigator with the multi-site management aspects of this trial. This includes, but is not limited to, study start-up, regulatory assistance (IRB submissions, amendments, and renewals), provision of template study forms (tracking and eligibility checklists, etc.), site qualification and activation, training, and overall project management. The MCU will provide tools to assist the study teams in conducting the trial appropriately and according to Good Clinical Practice Standards.

The MCU will ensure that all participating sites undergo remote training in which all key study personnel will be instructed study procedures, informed consent, source documentation requirements, safety and adverse event reporting, Good Clinical Practice guidelines and additional study related topics. This training will be conducted by the YCCI Study Monitor and/or MCU staff and documentation of completion will be required for all personnel.

Data and Safety Monitoring Committee

The Yale Cancer Center (YCC) Data and Safety Monitoring Committee (DSMC) will provide the primary oversight of data and safety monitoring. The Yale DSMC will review and monitor compliance, toxicity and deviations from this study. The committee is composed of clinical specialists with experience in oncology and who have no direct relationship with the study. Information that raises any questions about participant safety will be addressed with the Principal Investigator.

The DSMC will review this protocol bi-annually, at a minimum. Information to be provided to the committee includes: a study narrative by the PI, a summary DSMC report produced by OnCore (which includes participant accrual, response, trial status history, SAEs, adverse events, deviations and survival); audit results, and monitoring reports, as applicable. Other information (e.g., scans, laboratory values, etc.) will be provided upon request. Upon completing the review, the DSMC will approve whether the study should continue as planned, require modification/ amendment, or be placed on administrative hold with accrual temporarily suspended.

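### Inclusion criterion 10 joins the systolic and diastolic limits with *or*, so a patient with one component well above its limit meets it; it should say *and*

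*Combined protocol and SAP*

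**What the plan says.** Section 5.1.1, item 10, requires adequately controlled blood pressure, with or without medication, "defined as a systolic BP ≤ 150 or a diastolic BP ≤ 90 mmHg at screening"; the same test is repeated on Cycle 1 Day 1. The list that contains it is conjunctive: "Participants are eligible to be included in the study only if all of the following criteria apply".

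Three other places bear on blood pressure at entry:

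- Section 5.2.2.6: "Investigators should therefore ensure that participants enrolled to receive treatment with lenvatinib have BP of" 150/90 mm Hg or lower when they enter the study. Patients known to be hypertensive should also have been on a stable antihypertensive dose for at least a week before Cycle 1 Day 1.
- Section 5.2.2.4: "BP should be well-controlled prior to the start of lenvatinib". That sentence gives no numeric limit.
- Section 5.1.2, exclusion 24: uncontrolled hypertension, meaning systolic above 150 or diastolic above 90 mmHg, "in spite of an optimized regimen of antihypertensive medication".

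**The concern.** Two upper limits joined by *or* are satisfied as soon as one of them is met. Item 10 therefore accepts a patient with any systolic pressure if the diastolic is 90 or below, and any diastolic pressure if the systolic is 150 or below. That is looser than the 150/90 entry limit in Section 5.2.2.6.

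The stake is patient safety. Section 5.2.2.6 acknowledges that drugs blocking VEGF signaling can cause hypertension, and its withholding rule lists intracerebral hemorrhage among its examples. Every participant has brain metastases. Because item 10 names both screening and Cycle 1 Day 1, the same wording also governs the check on the day of the first dose. The trial is multi-site and supplies template eligibility checklists (Section 10.0). If item 10 were copied into one as it stands, the looser rule would reach sites without the correcting text in Section 5.2.2.6.

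**Working it through.** The plan has no figure to reproduce here. The check is logical and uses these rules, with S for systolic and D for diastolic pressure in mmHg:

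- Inclusion 10 as written (5.1.1): S ≤ 150 **or** D ≤ 90.
- Inclusion 10 as corrected: S ≤ 150 **and** D ≤ 90.
- Entry limit in 5.2.2.6: 150/90 or below, that is, both components within limits.
- Exclusion 24 (5.1.2): (S > 150 or D > 90) and the regimen is already optimized.

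**Step 1: two readings against item 10 and Section 5.2.2.6.**

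- 185/88: 185 ≤ 150 is false and 88 ≤ 90 is true, so item 10 is met. Section 5.2.2.6 fails, because 185 > 150.
- 145/110: 145 ≤ 150 is true and 110 ≤ 90 is false, so item 10 is met. Section 5.2.2.6 fails, because 110 > 90.

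**Step 2: does exclusion 24 close the gap?** Take four illustrative readings, each with the regimen optimized or not. *Eligible* here means passing inclusion 10 and not being caught by exclusion 24.

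| Reading | Regimen optimized | Item 10 with *or* | Exclusion 24 applies | Eligible as written | Item 10 with *and* | Eligible after fix |
|---|---|---|---|---|---|---|
| 145/88 | no | met | no | yes | met | yes |
| 145/88 | yes | met | no | yes | met | yes |
| 185/88 | no | met | no | **yes** | not met | no |
| 185/88 | yes | met | yes | no | not met | no |
| 145/110 | no | met | no | **yes** | not met | no |
| 145/110 | yes | met | yes | no | not met | no |
| 185/110 | no | not met | no | no | not met | no |
| 185/110 | yes | not met | yes | no | not met | no |

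As written, 4 of 8 cells are eligible; after the fix, 2 of 8. The difference, 4 − 2 = 2, consists of the cells with exactly one high component and a regimen that is not optimized. The count locates the gap and says nothing about how many patients fall in it.

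**Step 3: which connective was intended?** The negation of S > 150 or D > 90 is S ≤ 150 and D ≤ 90. Item 10 has the inequalities of exclusion 24 reversed but the same *or*. Section 5.2.2.6 also joins its restart limits with *and*: after an interruption for persistent or recurrent hypertension, lenvatinib may resume only at systolic 150 or below and diastolic 95 or below. On a literal reading of item 10, a patient at 185/88 could enter but could not restart.

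**The case against.** The strongest reply is that the intended limit is plain and largely enforced elsewhere. Section 5.2.2.6 tells investigators to ensure 150/90 at entry, Section 5.2.2.4 asks for good control before lenvatinib, and exclusion 24 tests each component correctly. A site can comply with both item 10 and Section 5.2.2.6, and doing so yields 150/90. If Section 5.2.2.6 is treated as part of the entry rule, 2 of 8 cells are eligible both before and after the change, a difference of 0.

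Much of this stands. Section 5.2.2.6 says investigators should ensure the limit, which is weaker than a formal requirement; item 10 is the looser of two rules rather than one that makes the other impossible to follow; and an experienced investigator would probably read it as 150/90. The 2-cell difference applies to the Section 5.1 criteria alone.

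It does not rescue the criterion. Section 5.2.2.6 is a toxicity-management section that someone screening for eligibility may not consult. Exclusion 24 misses patients who are not on an optimized regimen. The one-week stable-dose rule covers only known hypertensives. Exclusions 23 (bleeding risk) and 29 (investigator's judgment) contain no pressure limit, and exclusion 3 concerns overt hemorrhage from CNS metastases. The withholding rule reads "Lenvatinib should be withheld in any instance where a participant is at imminent risk to develop a hypertensive crisis"; it also covers patients judged likely to suffer serious harm from uncontrolled pressure, so it depends on judgment. For confirmed pressures of at least 160 systolic or 100 diastolic in patients not yet on antihypertensives, the same section says to continue study drug and start treatment.

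**Conclusion.** The concern holds: item 10 is wrong as written. Taken literally with exclusion 24, it admits patients with exactly one component above its limit who are not on an optimized regimen. How many such patients would present is unknown, and this review does not claim that any would be enrolled or dosed. The conclusion rests on a literal reading of item 10 and on taking exclusion 24's qualifier at face value.

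The matter is one of eligibility wording and safety. The Simon designs (13 then 27 patients in melanoma, 18 then 29 in RCC), their error rates and all analyses are unaffected. The sponsor should correct it.

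**What to change.** In inclusion criterion 10, replace *or* with *and*: systolic BP ≤ 150 **and** diastolic BP ≤ 90 mmHg, at screening and on Cycle 1 Day 1. This matches the limit in Section 5.2.2.6 and makes item 10 the exact complement of the pressure limits in exclusion 24. Exclusion 24 needs no edit, since every inclusion criterion must be met.

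Confirm that the eligibility checklist uses the same wording. Its content is not in the documents, so it may already be right.

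The cost is one word plus any checklist change, made through an amendment that needs IRB approval (Section 10.0). A few patients may need their pressure controlled before entry, which Sections 5.2.2.4 and 5.2.2.6 already ask for.

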5.1.2 Participant Exclusion Criteria

Participants are excluded from the study if any of the following criteria apply:

1. Symptomatic melanoma or RCC brain metastases at the time of therapy initiation.
2. Active use of corticosteroids to control CNS symptoms, unless steroid requirement has been decreasing and currently on $\leq 10\text{ mg}$ of prednisone or its equivalent without CNS symptoms for 7 days or more.
3. Overt hemorrhage from CNS metastases.
4. Presence of leptomeningeal disease.

5. Unable to undergo MRI imaging (either due to such conditions as inability to lie flat for the scan duration, incompatible medical devices at risk for malfunction, and foreign metal objects that pose a safety risk for imaging).
6. A WOCBP who has a positive urine pregnancy test within 72 hours prior to allocation (see Appendix 3). If the urine test is positive or cannot be confirmed as negative, a serum pregnancy test will be required.
7. Has received anti-cancer therapy including investigational agents within 14 days prior to allocation or less than 4 weeks from prior immunomodulating antibody (excluding anti-PD1/PD-L1).

Note: Participants must have recovered from all AEs due to previous therapies to \leq Grade 1 or baseline. Participants with \leq Grade 2 neuropathy, rash, and/or alopecia may be eligible.

Note: If participant received major surgery, they must have recovered adequately from the toxicity and/or complications from the intervention prior to starting study treatment.

8. Has received prior CNS radiotherapy within 1 week of start of study treatment. Participants must have recovered from all radiation-related toxicities and not require corticosteroids.
9. Has received a live vaccine within 30 days prior to the first dose of study drug. Examples of live vaccines include, but are not limited to, the following: measles, mumps, rubella, varicella/zoster (chicken pox), yellow fever, rabies, Bacillus Calmette–Guérin (BCG), and typhoid vaccine. Seasonal influenza vaccines for injection are generally killed virus vaccines and are allowed; however, intranasal influenza vaccines (eg, FluMist®) are live attenuated vaccines and are not allowed.
10. Is currently participating in or has participated in a study of an investigational agent or has used an investigational device within 4 weeks prior to the first dose of study treatment.

Note: Participants who have entered the follow-up phase of an investigational study may participate as long as it has been 4 weeks after the last dose of the previous investigational agent.

11. Has a diagnosis of immunodeficiency or is receiving chronic systemic steroid therapy (in doses exceeding 10 mg daily of prednisone equivalent) or any other form of immunosuppressive therapy within 7 days prior to the first dose of study drug.
12. Has a known additional malignancy that is progressing or is requiring active treatment.
13. Has active autoimmune disease that has required systemic treatment in the past 3 months or a documented history of clinical severe autoimmune disease, or a syndrome that requires chronic systemic steroids or immunosuppressive agents. Replacement therapy (eg., thyroxine,

insulin, or physiologic corticosteroid replacement therapy for adrenal or pituitary insufficiency with prednisone ≤ 10 mg or the equivalent, etc.) is not considered a form of systemic treatment. Subjects with thyroid disease or vitiligo will not be excluded from the study.

14. Has presence of gastrointestinal condition including malabsorption, gastrointestinal anastomosis, or any other condition that might affect the absorption of lenvatinib.
15. Has a pre-existing Grade ≥ 3 gastrointestinal or non-gastrointestinal fistula.
16. Serious non-healing or dehiscing wound.
17. Has radiographic evidence of major blood vessel invasion/infiltration. The degree of tumor invasion/infiltration of major blood vessels should be considered because of the potential risk of severe hemorrhage associated with tumor shrinkage/necrosis following lenvatinib therapy.
18. Has clinically significant hemoptysis or tumor bleeding within 2 weeks prior to the first dose of study drug.
19. Has clinically significant cardiovascular disease within 6 months of the first dose of study intervention including New York Heart Association Class III or IV congestive heart failure, unstable angina, myocardial infarction, cerebral vascular accident, or cardiac arrhythmia associated with hemodynamic instability.

Note: Medically controlled arrhythmia is permitted.
20. Has prolongation of QTc interval (calculated using Fridericia's formula) to >480 msec.
21. New York Heart Association congestive heart failure of grade II or above, unstable angina, myocardial infarction within the past 6 months, or serious cardiac arrhythmia associated with significant cardiovascular impairment within the past 6 months.
22. Has urine protein ≥ 2 g/24-hour.

Note: Participants with $>1+$ proteinuria on urine dipstick will undergo 24-hour urine collection for quantitative assessment of proteinuria.
23. Evidence of a bleeding diathesis, risk for severe hemorrhage, or clinically significant coagulopathy.
24. Uncontrolled hypertension (systolic BP >150 mmHg or diastolic BP >90 mmHg) in spite of an optimized regimen of antihypertensive medication.

25. Has a history of (non-infectious, non-radiation-induced) pneumonitis not responsive to steroids or has current pneumonitis. Patients will also be excluded if there are respiratory issues including active infection or require supplemental oxygen for activities of daily living.
26. Has an active infection requiring systemic therapy.
27. Has a known history of Human Immunodeficiency Virus (HIV).
28. Has a known history of Hepatitis B or known active Hepatitis C virus infection.

Note: No testing for Hepatitis B and Hepatitis C is required unless mandated by local health authority.

29. Has a history or current evidence of any condition, therapy, or laboratory abnormality that might confound the results of the study, interfere with the subject's participation for the full duration of the study, or is not in the best interest of the subject to participate, in the opinion of the treating investigator.
30. Has known psychiatric or substance abuse disorders that would interfere with cooperation with the requirements of the trial.
31. Is pregnant or breastfeeding or expecting to conceive or father children within the projected duration of the study, starting with the screening visit through 120 days after the last dose of trial treatment.
32. Women of child-bearing potential who are unwilling to or unable to use an acceptable method of contraception to avoid pregnancy for the entire study and for at least 5 months after cessation of study drug or have a positive pregnancy test at screening or baseline, or who are pregnant or breast feeding.

